1.3.5 Predicting ECT-Induced Cognitive Impairment through Multi-Scale Entropy

Additional data from our group suggests that resting EEG can be used to predict cognitive adverse effects following a course of seizure therapy. We obtained resting-state EEG from 34 patients receiving MST or ECT, and employed multi-scale entropy to quantify the complexity of brain temporal dynamics before and after seizure therapy. Temporal complexity represents the temporal fluctuations in resting state neurophysiological signals. The more complex the signal, the less recurring temporal patterns it contains. In ECT, but not MST, complexity of brain temporal dynamics in coarse time scales was significantly increased. In a subset of 19 patients we obtained scores of global cognitive function using the Montreal Cognitive Assessment (MoCA)[70] before and after ECT (n = 6) and MST (n =13) treatment. We found that increased complexity in coarse time scales derived through multi-scale entropy from EEG predicted change in MoCA with over 90 percent accuracy.

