3.0 OBJECTIVES AND HYPOTHESES

Primary objective: To assess the efficacy and cognitive adverse effects of MST compared to RUL-UB ECT in patients with depression.

Primary hypothesis/combined effectiveness endpoint: (1) MST will result in remission rates on the 24-item Hamilton Rating Scale for Depression (HRSD-24) that is non-inferior to that of RUL-UB ECT; **AND** (2) MST will have a superior cognitive adverse effect and tolerability profile compared to RUL-UB ECT as assessed with the Autobiographical Memory Test (AMT).

Secondary objective: To assess the efficacy MST compared to RUL-UB ECT in ameliorating suicidal ideation in patients with depression.

Secondary hypothesis/effectiveness endpoint: MST will have a non-inferior remission rate on the SSI compared to RUL-UB-ECT in patients with depression.

Tertiary objective: To refine and develop candidate neurophysiological biomarker, cortical inhibition (CI), using combined transcranial magnetic stimulation and electroencephalography (TMS-EEG) that may predict response to treatment using remission of suicidal ideation as a meaningful clinical indicator.

Tertiary hypothesis/effectiveness endpoint: (1) Change in CI in the DLPFC following MST will significantly predict SSI reduction; (2) Following MST and ECT, increased complexity in course time scales derived through multi-scale entropy will be associated with change in the AMT scores in patients with depression.

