5.4. Resting EEG and Multi-Scale Entropy

Ten minutes of resting-state eyes closed EEG data are recorded prior to the start and after a course of ECT or MST treatment. EEG will be through a 64-channel NeuroScan EEG system. Acquired data will be imported into MATLAB (The MathWorks. Inc. Natick, MA, USA) for preprocessing. The open source signal processing functions in EEGLAB toolbox will be used for data import and preprocessing. Multi-scale entropy will be examined across all electrodes using two steps [101]: The *coarse-graining* process and the calculation of the sample entropy (*SampEn*) for each coarse-grained time series. First, for a given time series $\{x_1, x_2, \dots, x_N\}$, the multiple coarse-grained time series $\{y_1^{(\tau)}, y_2^{(\tau)}, \dots, y_N^{(\tau)}\}$ at scale factor τ are calculated by averaging the data points within non-overlapping windows of increasing length τ . Each element of the coarse-grained time series $y_j^{(\tau)}$, will be calculated as $y_j^{(\tau)} = \frac{1}{\tau} \sum_{i=(j-1)\tau+1}^{j\tau} x_i$, where τ represents the scale factor and $j \left(1 \leq j \leq \frac{N}{\tau}\right)$ represents the time index of the element. The length of each coarse-grained time series is M , where $M = \text{floor} \left(\frac{N}{\tau}\right)$. Second, the degree of predictability is measured for each of the multiple coarse-grained time series $\{y_1^{(\tau)}, y_2^{(\tau)}, \dots, y_N^{(\tau)}\}$ using SampleEn. SampleEn is calculated as $\text{SampleEn}(r, m, M) = -\ln(C(m+1)/C(m))$, where $C(m)$ is the total number of pairs of m consecutive similar data points, $C(m+1)$ is the total number of pairs of $m+1$ consecutive similar data points in the multiple coarse-grained time series. SampleEn quantifies the variability by estimating the predictability of amplitude patterns across a time series. Two consecutive data points will be used for data matching ($m = 2$) and data points will be considered to match if their absolute amplitude difference is less than 0.15% ($r = 0.15$) of standard deviation of time series. Multi-scale entropy will be calculated for two 20s continuous epochs according to Farzan et al. and then averaged [102].

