5.8.4 Tertiary Outcome Analysis: Neurophysiological Data

We will investigate the relationship between change in CI and SSI reduction by calculating the area under the receiver operating characteristic (ROC) curve (AUC) as discussed above (Section 1.3.4). ROC analysis is used in medicine to evaluate diagnostic test accuracy. The ROC involves plotting the sensitivity (true positive rate) versus 1-specificity (false positive rate). The ROC AUC predicts performance of the diagnostic test. An AUC of 1 represents perfect prediction with optimal sensitivity and specificity while 0.5 suggests that the diagnostic test is no better than chance at diagnostic prediction. For our purposes, the ROC AUC then corresponds to the change in CI that optimally distinguishes MST and ECT remitters from non-remitters (defined as a zero score on the SSI). Based on our preliminary data described above (Section 1.3.4), we will use change in CI (defined as the LICl TMS-EEG response) to distinguish MST and ECT SSI remitters from non-remitters using a ROC AUC of >0.85 on all frontal electrodes using a false detection rate correction that is applied to all frontal electrodes.

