5.8.5 Multi-scale entropy analysis

For this hypothesis, we will follow the analytic methods described in section 5.4. We will investigate the relationship between complexity in course time scales derived through multi-scale entropy and change in the AMT scores in patients with depression. The ROC AUC will correspond to the level of multi-scale entropy at baseline that optimally distinguishes MST and ECT memory performance using a receiver operator area under the curve of >0.85 across all frontal electrodes.

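### The multi-scale entropy ROC uses baseline entropy although the hypothesis concerns the increase after treatment, and the matching tolerance is given as two values 100-fold apart

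*Combined protocol and SAP*

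**What the plan says.** Section 3.0, tertiary hypothesis 2: "Following MST and ECT, increased complexity in course time scales derived through multi-scale entropy will be associated with change in the AMT scores". The pilot in Section 1.3.5 measured entropy before and after seizure therapy and reports: "We found that increased complexity in coarse time scales derived through multi-scale entropy from EEG predicted change in MoCA with over 90 percent accuracy".

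Section 5.4 provides the data for a change score: "Ten minutes of resting-state eyes closed EEG data are recorded prior to the start and after a course of ECT or MST treatment". The same section sets the template length at m = 2 and defines sample entropy as −ln(C(m+1)/C(m)). Data points are "considered to match if their absolute amplitude difference is less than 0.15", and this figure is followed directly by a percent sign, then by r = 0.15 in brackets, as a share of the SD of the series.

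Section 5.8.5 presents itself as the analysis of this hypothesis. It first says that complexity will be related to AMT change, without a time point. It then specifies its only statistic: "The ROC AUC will correspond to the level of multi-scale entropy at baseline that optimally distinguishes MST and ECT memory performance", with an AUC above 0.85 over the frontal electrodes as the criterion. The neighbouring cortical-inhibition analysis in Section 5.8.4 is built on a change score: "the ROC AUC then corresponds to the change in CI that optimally distinguishes MST and ECT remitters from non-remitters". It also applies a false-detection-rate correction over the frontal electrodes. Section 5.8.5 states no such correction.

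**The concern.** A single pre-treatment value cannot show an increase. If the analysis is run as Section 5.8.5 specifies it, the result answers whether baseline complexity predicts memory outcome. That is a reasonable question, but it is not tertiary hypothesis 2. If both texts stay, the choice between baseline and change can be made after the data are seen.

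An ROC also needs two outcome classes. Section 5.8.5 refers only to memory performance, so the cut-off that separates cases from non-cases is left open as well.

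The tolerance decides which points count as matches and so determines the entropy value. Two values 100-fold apart in one sentence leave the measure itself ambiguous.

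**Working it through.** **1. Predictor, side by side**

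| Place | Entropy quantity |
|---|---|
| Section 3.0, tertiary hypothesis 2 | increase following treatment |
| Section 1.3.5, pilot | increase, from recordings before and after treatment |
| Section 5.4, recording | EEG before and after the course |
| Section 5.8.5, first mention | complexity, no time point |
| Section 5.8.5, ROC | level at baseline |
| Section 5.8.4, parallel analysis | change (in cortical inhibition) |

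Only the ROC sentence says baseline, and it is the only statistic specified.

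**2. ROC outcome.** Section 5.8.5 gives no cut-off. Section 5.8.1 (Stage 2) already defines a binary one, a worsening of at least 25% on the AMT total score, but Section 5.8.5 does not refer to it.

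**3. Tolerance, unit check.** 0.15% of the SD is 0.0015 SD, whereas r = 0.15 means 0.15 SD. The ratio is 0.15 / 0.0015 = 100.

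**4. What the literal percentage does.** With m = 2, sample entropy is −ln(C(3)/C(2)), which is undefined when C(3) = 0. The epochs last 20 s (Section 5.4). The documents give neither sampling rate nor scale factors, so I assume 250, 500 and 1000 Hz and scale factors τ from 1 to 70.

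For white noise, two independent points lie within r SD of each other with probability of about r/√π, so E[C(3)] ≈ M(M−1)/2 × (r/√π)³. At r = 0.0015, (0.0015/1.772)³ = 6.06 × 10⁻¹⁰. At r = 0.15 it is 100³ = 10⁶ times larger. At τ = 1:

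| Rate | M | Pairs | E[C(3)], 0.0015 SD | E[C(3)], 0.15 SD |
|---|---|---|---|---|
| 250 Hz | 5,000 | 12,497,500 | 0.008 | about 7,600 |
| 500 Hz | 10,000 | 49,995,000 | 0.03 | about 30,300 |
| 1000 Hz | 20,000 | 199,990,000 | 0.12 | about 121,000 |

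Simulated white noise at 0.15 SD gave mean C(3) of 29,954 (500 Hz) and 119,409 (1000 Hz), in line with the formula.

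Real EEG is autocorrelated, so a 1/f signal with an alpha peak (1–50 Hz) was also simulated, coarse-grained as in Section 5.4, with the tolerance fixed at the SD of the original series. Runs with undefined entropy at 0.0015 SD, out of 40:

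| τ | 250 Hz | 500 Hz | 1000 Hz |
|---|---|---|---|
| 1 | 37 | 6 | 0 |
| 5 | 40 | 40 | 39 |
| 10 | 40 | 40 | 39 |
| 20 to 70 | 40 | 40 | 40 |

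White noise at τ of 10 or more gave 39 or 40 of 40 at every rate. At 0.15 SD no run was undefined (0 of 5 in every setting, both signals). Mean C(3) at τ of 20 or more ranged from about 50 to about 24,000 matches.

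**The case against.** The sentence in Section 5.8.5 that links complexity to AMT change is not limited to baseline, and the section refers back to Section 5.4, where both recordings are planned. Section 1.3.5 also introduces the work as using resting EEG to predict cognitive adverse effects, so a baseline predictor may be partly intended. This stands to the extent that a reader should not infer that the hypothesis is untestable: the data to test it will exist. It does not remove the mismatch, because the one statistic specified uses the wrong time point for the hypothesis it names.

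A reader might also take the ROC sentence to mean that entropy separates the MST arm from the ECT arm. Under randomisation a pre-treatment measure would then have an expected AUC of 0.5. The documents do not support that reading. Section 5.8.4 uses the same construction, in which MST and ECT describe the patients and the classes are remitters and non-remitters. What remains is the undefined memory outcome.

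On the tolerance, an analyst who follows the formula would enter r = 0.15, and the percent sign is most likely stray. That stands. The inconsistency is one of wording and does not show that the measure cannot be computed.

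**Conclusion.** The mismatch holds on the face of the documents. The specified ROC tests baseline prediction, the hypothesis concerns the increase after treatment, and the binary outcome is missing. No simulation is needed for this part.

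The tolerance point is a 100-fold contradiction within one sentence. A reader might infer that sample entropy will be undefined throughout. That goes too far, for two reasons: the same sentence also gives r = 0.15, at which every run was finite; and even at 0.0015 SD the EEG-like signal gave a value in all 40 runs at 1000 Hz and τ = 1. The supported statement is narrower. Read literally, the percentage leaves entropy undefined in nearly all simulated epochs at τ of 10 or more, the kind of coarse scale that the hypothesis concerns. This rests on assumed sampling rates, scale range and signal models.

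Severity is minor. One tertiary hypothesis is affected; the two-stage primary analysis and the sample size are not.

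**What to change.** In Section 5.8.5:
- Define the predictor as coarse-scale entropy after treatment minus before treatment.
- Define the ROC outcome as AMT worsening of 25% or more, by reference to Section 5.8.1, Stage 2.
- Apply over the frontal electrodes the correction that Section 5.8.4 already uses.
- If a baseline-entropy ROC is also wanted, list it as a separate exploratory analysis.

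In Section 5.4, state one tolerance: 0.15 × SD.

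Optional: a regression of AMT change on entropy change, adjusted for arm. In the pilot complexity rose with ECT but not with MST, and the primary hypothesis expects AMT to favour MST, so a pooled association could partly reflect arm. This would be an addition, not a correction.

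The cost is a short rewrite of Section 5.8.5 and one edit in Section 5.4. Resting EEG and AMT are already collected before and after the course, so no new data are needed. A change score does require both recordings, so participants with only one would not contribute to it.

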
An adjusted analysis will be performed using generalized linear models for binary data. Study site will be included as well as clinical variables known to be associated with remission (see again Senn et al.[105] and Pocock et. al.[104]). The following variables will be included in the analysis, which have been shown to be related to response/remission in this population: number of failed antidepressant trials, duration of most recent depressive episode, number of major depressive episodes, and benzodiazepine use (in lorazepam equivalents). The purpose of the adjusted analysis is to ensure the non-inferiority finding is consistent between an unadjusted analysis and one in which predictors of outcome are controlled for. This consistency will be examined in two ways. First, the unadjusted odds ratio and 95% confidence interval will be compared with the adjusted for consistency. Second, the fitted logistic regression model will be used to estimate the probability of response for each subject. An adjusted difference in proportions will be estimated by averaging the predicted probabilities within group and taking the difference. A bootstrap will then be used to generate a distribution of this measurement from which the bias corrected percentiles can be obtained to compare with the 15% non-inferiority margin.

Stage 2 Analysis

In terms of cognitive superiority, we will use the autobiographical memory test (AMT). The binary outcome is defined as a worsening of $\geq 25\%$ on the AMT total score. The hypothesis to be tested is $H_0: \pi_{ECT} - \pi_{MST} = 0$ versus $H_1: \pi_{ECT} - \pi_{MST} \neq 0$ where π_{ECT} and π_{MST} are the probabilities of deterioration in the ECT and MST groups respectively. This primary analysis will be ITT. The hypothesis will be tested with a chi-square test. The absolute risk difference and 95% confidence interval will be computed using standard methods. Secondary analyses will follow a similar approach as in stage 1.

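### Section 5.8.5 does not test tertiary hypothesis 2: the hypothesis is an association between entropy and change in AMT scores, but the only analysis is a ROC with no defined yes/no outcome and an AUC >0.85 bar.

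*Combined protocol and SAP*

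**What the plan says.** Section 3.0 words the second tertiary hypothesis as an association: after MST and ECT, "increased complexity in course time scales derived through multi-scale entropy will be associated with change in the AMT scores". It gives no cut-off on the AMT.

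Section 5.8.5 opens with the same aim: "We will investigate the relationship between complexity in course time scales derived through multi-scale entropy and change in the AMT scores". It then gives one method, a ROC curve. The predictor is "the level of multi-scale entropy at baseline", and the curve is to show the level that "optimally distinguishes MST and ECT memory performance using a receiver operator area under the curve of >0.85 across all frontal electrodes". The section describes no correlation or regression, and it does not say which participants form the two classes.

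Three other places bear on this:

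- Section 5.8.1, Stage 2, has the plan's only two-class AMT outcome. "The binary outcome is defined as a worsening of" 25% or more on the total score. Section 5.8.5 does not refer to it.
- Section 5.8.4, the parallel ROC analysis of cortical inhibition, does define its classes, "remitters from non-remitters (defined as a zero score on the SSI"). It also handles multiplicity, "using a false detection rate correction that is applied to all frontal electrodes". Section 5.8.5 repeats neither element.
- Section 5.4 has resting EEG "recorded prior to the start and after a course of ECT or MST treatment", so change in entropy can be computed. AMT is scheduled at baseline and end of treatment (section 5.1.5 and Appendix A).

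**The concern.** A ROC curve answers a different question from the one posed. It asks how well a marker separates two groups; the hypothesis asks whether entropy and AMT change move together. Three problems follow.

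- With no class defined, the analysis cannot be run from the text without a further decision, and that decision could be taken after the data are seen.
- An AUC above 0.85 is far more than an association. A moderate, real relation would be recorded as a failure.
- Any split of the AMT discards the size of the change, although the graded scores are already collected.

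Section 1.3.1 lists quantitative EEG as a probe of the mechanism of ECT-induced cognitive impairment among the study's innovations. Section 5.8.5 is the only analysis of it.

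**Working it through.** **Plan's own figure.** There is no power or sample-size statement for this analysis to reproduce. The 260 participants in section 5.7.1 are sized for HRSD-24 remission. The only figure in section 5.8.5 is AUC >0.85.

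**Assumptions, none of them in the documents.** Entropy X and AMT worsening Y are bivariate normal with correlation r; one electrode; two-sided 0.05. A proportion q counts as worsened, W = 1 if Y > Φ⁻¹(1−q). The number with paired EEG is unknown. Section 5.5 keeps participants who cannot complete biomarker testing, and section 8.5 makes neurophysiology conditional during COVID-19, so I take n from 80 to 260.

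**Step 1: what AUC >0.85 demands.** AUC = P(X of a worsened participant > X of a participant not worsened).

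| r | AUC, q=25% | AUC, q=50% |
|---|---|---|
| 0.2 | 0.596 | 0.590 |
| 0.3 | 0.644 | 0.636 |
| 0.5 | 0.742 | 0.730 |
| 0.7 | 0.842 | 0.829 |

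Solving for AUC = 0.85 gives r of about 0.70-0.74 for q from 20% to 50%.

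**Step 2: how often the stated rule is met.** Observed AUC >0.85, 4,000 simulated trials per setting, q = 25% or 50%, n = 80, 130 and 260:

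- r = 0.2 or 0.3: at most 0.1%.
- r = 0.5: at most 4%, the highest value being at n=80.
- r = 0.7: 22% to 45%.

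If fewer than 20% worsen, the correlation required is somewhat lower, and small samples pass by chance more often.

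**Step 3: the cost of the split alone.** Here the cut outcome is tested as AUC against 0.5. The plan does not state that test; it is used only to separate the effect of splitting from the effect of the 0.85 bar.

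Splitting shrinks the usable correlation to r·φ(z_q)/√(q(1−q)):
- q = 25%: 0.318/0.433 = 0.73, so 0.73r.
- q = 50%: 0.399/0.5 = 0.80, so 0.80r.

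Full-score power is Φ(atanh(r)·√(n−3) − 1.96). For n=150, r=0.25 this is Φ(0.2554 × 12.12 − 1.96) = Φ(1.14) = 87%. With the split, power is 41%, 54%, 63% and 68% for q = 10%, 20%, 30% and 50%.

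Other settings (simulation; Pearson test on the full score):

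| n | r | Full score | Split, q=25% | Split, q=50% |
|---|---|---|---|---|
| 80 | 0.3 | 79% | 50% | 56% |
| 80 | 0.5 | 99.8% | 92% | 96% |
| 130 | 0.3 | about 94% | 70% | 77% |
| 130 | 0.5 | 100% | 99% | 99.7% |
| 260 | 0.2 | 90% | 65% | 71% |
| 260 | 0.3 | 99.9% | 94% | 97% |
| 260 | 0.5 | 100% | 100% | 100% |

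The split matters for weak associations and small subsets. The 0.85 rule matters nearly everywhere below r = 0.7.

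**The case against.** **ROC suits the purpose.** The tertiary objective is to develop a biomarker, and section 1.3.5 is about predicting cognitive impairment. A demanding discrimination benchmark is reasonable for that, and a correlation of 0.25 would have little predictive use. This stands as a reason to keep the ROC. It does not make AUC >0.85 a test of the association that section 3.0 states.

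**The pilot points to a strong relation.** Section 1.3.5 reports over 90 percent accuracy. That is the documents' only guide to effect size, and under a strong relation the split costs little. But it rests on 19 patients (6 ECT, 13 MST) and on the MoCA, not the AMT, so it cannot by itself justify expecting an AUC above 0.85 here.

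**Stronger readings that the documents do not support.**

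- A reader might infer that section 5.8.5 splits the AMT at 25% worsening, so that 24% worse is grouped with improved. It never adopts that cut. The matching phrase in section 5.8.4 suggests that MST and ECT describes the pooled patients, but the classes could even be read as the treatment arms, in which case AMT change would not be analysed at all. The documented fault is that the class is undefined.
- A reader might infer that splitting the outcome alone makes a real association likely to be missed. At n=260 and r=0.3 with 30-50% worsened, the loss is below 5 percentage points. The 0.85 rule is what makes a miss likely.
- A reader might infer that baseline AMT is ignored. Any change or percentage worsening uses it; it is only absent as a covariate.

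**Conclusion.** The point holds in this form: followed as written, section 5.8.5 does not test tertiary hypothesis 2. The ROC lacks a defined outcome, and its success rule measures strong discrimination. With 20-50% worsened, that rule corresponds to a correlation of about 0.70-0.74, so r = 0.3 would almost never meet it and r = 0.5 would do so in a few percent of trials or fewer. Loss of power from splitting the AMT is a secondary issue. It is material at, for example, n=150 and r=0.25 (87% against about 41-68%). It is small at n=260 with r=0.3 and 30-50% worsened, and also at r = 0.5 unless the subset is very small or few participants worsen.

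These sizes rest on assumed n, r, proportion worsened, normality and a single electrode. They read the rule as applying to the observed AUC. Requiring every frontal electrode to pass would be stricter, and accepting any one electrode would be looser. The mismatch between hypothesis and analysis depends on none of this. As a tertiary analysis, it does not touch the primary conclusion.

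**What to change.** In section 5.8.5:

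1. **Test.** Make the test of tertiary hypothesis 2 a linear or rank-based regression of end-of-treatment AMT total score on the coarse-scale entropy predictor, adjusted for baseline AMT and site. Report the slope with a 95% CI.
2. **Predictor.** Reconcile section 3.0 (increased complexity following treatment) with section 5.8.5 (level at baseline) and name one as the predictor for the test. Both can be computed from the planned recordings.
3. **Arm.** Report the slope with and without adjustment for arm. In the pilot, complexity rose with ECT but not MST, so adjusting for arm removes between-arm signal and changes the question when change in entropy is the predictor.
4. **Multiplicity.** Apply the section 5.8.4 false-discovery correction over the frontal electrodes.
5. **ROC.** Keep it as a descriptive secondary result. Define its class as AMT worsening of 25% or more, as in Stage 2, and treat AUC >0.85 as a benchmark of predictive usefulness only.

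The cost is SAP wording and a little more analysis of data already collected. The headline becomes a slope in place of a discrimination figure, which the retained ROC still supplies. The power figures above are for an unadjusted single-electrode correlation and should not be quoted as the power of this adjusted, multiplicity-corrected model.
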